11.1.5 EVALUABLE DATA FOR ANALYSIS

All data will be evaluable for the study safety and effectiveness analysis.

11.1.6 ANALYSIS POPULATION

Effectiveness Analysis population: The effectiveness analysis and exploratory effectiveness endpoints will be based on all data from all subjects in this investigation with at least one paired glucose reading (one Sensor with one reference glucose). The Eversense® 180 CGM System and reference readings are compared by pairing each reference reading with the first Sensor reading that occurred up to 5 minutes after sample acquisition.

Safety Analysis Population: Safety analysis will be based on all subjects that undergo the sensor insertion in this investigation.

11.1.7 SUBJECT ACCOUNTABILITY

A Subject Accountability flow diagram will account for all subjects from informed consent through end of study and includes any early explants or withdrawals (Figure 1 in APPENDIX 1).

11.1.8 STUDY DEMOGRAPHICS ANALYSIS

Descriptive statistics will be provided for demographic variables and other baseline characteristics, such as age, gender, race, BMI, diabetes type, insulin therapy, history of ketoacidosis, and history of hypoglycemia.

11.1.9 TABULATION OF INVESTIGATIONAL DEVICE DEFICIENCIES

11.1.9.1 TRANSMITTER DEFICIENCIES

A tabulation of all reported transmitter device deficiencies will be presented (Table 1 in APPENDIX 1).

11.1.9.2 SENSOR DEFICIENCIES

A tabulation of all reported sensor device deficiencies will be presented (Table 2 in APPENDIX 1).

11.2 SAFETY ENDPOINTS

The safety endpoint is the incidence of device-related or insertion/removal procedure-related serious adverse events (SAEs) in the clinic and during home use through 180 days post-insertion.

An Adverse Event is considered 'related' if the relatedness is categorized as 'possibly related', or 'related'. The assessment of seriousness and relatedness made by the Medical Monitor will be used for analysis. The numbers of SAEs and the percentage of patients with SAEs will be reported for each SAE type that is observed, identified as device-related, procedure-related or unrelated to the study (Table 3 in APPENDIX 1). The count and proportion of patients experiencing at least one device-related or procedure-related SAE will be presented. No inferential statistical analysis will be performed.

Other safety endpoints include:

- Incidence of insertion/removal procedure or device-related adverse events in the clinic and during home use.
- Incidence of all adverse events in the clinic and during home use.
- Incidence of hospitalizations due to hypoglycemia, hyperglycemia or ketoacidosis occurring during home use.

- Incidence of reported hypoglycemic and hyperglycemic events occurring during home use.

For each of the adverse event (AE or SAE) categories above, the numbers of AEs and the percentage of patients with AEs will be reported for each AE type that is observed and be stratified by the target age enrollment categories (Tables 4A-4E in APPENDIX 1). A listing (Table 5 in APPENDIX 1) will be prepared that identifies each patient with a reported AE or SAE, and relevant information including date of onset, severity level, seriousness, relatedness to the device or procedure, classification as anticipated or unanticipated, corrective action(s) taken, and resolution status (resolved or ongoing).

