Causality: The causal relationship should be determined with respect to the investigational device, the insertion or removal procedure, or other study-related procedures.

None: The event is not associated with the device or procedure. There is no relation between the event and the device or procedure.

Possibly Related: The temporal sequence between the device or procedure and the event is such that the relationship is not unlikely or there is no contradicting evidence that can reasonably explain the Subject's condition. There is a possibility of any relation between the event and the device or procedure.

Related: The temporal sequence is relevant, or the event abates upon device application completion/removal or the event cannot be reasonably explained by the patient's condition or comorbidities. The event is related or most likely associated with the device or procedure.

Unknown: There is no evidence or relevant data available to assess the relationship between the event and the device or procedure.

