9.3 ADVERSE EVENT REPORTING

All adverse events (AEs) will be reported by the Investigator and reviewed by the Sponsor in compliance with applicable regulations. Site will follow local IRB reporting requirements for reporting to IRB.

All SAEs must be reported to Sponsor as soon as possible but in no event later than 3 days after learning of the event. Include Study ID, Study Site, Adverse Event, causal relationship to device and procedure (insertion/removal/other study procedure), seriousness, expectedness, and provide source documentation as soon as available. The AE form of the CRF must be completed within 3 days of awareness for all SAEs.

All UADEs must be reported to the Sponsor and to the reviewing IRB as soon as possible, but in no event later than 3 days after the Investigator first learns of the event. The AE form of the CRF must be completed as soon as possible but no later than 3 days for all UADEs.

All adverse events classified as possibly related or related to the device or procedure will be reported to Senseonics as soon as possible but no later than 3 days of learning of events.

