6.6 Analysis of Study Endpoints

6.6.1 Safety Endpoints

The primary safety endpoint is defined as the incidence rate of device-related or procedure-related (from insertion or removal of the Sensor) serious adverse events occurring up to 180 days after the insertion procedure. The assessment of seriousness and relatedness will be made by the Medical Monitor. An adverse event is classified as “related” if its relatedness is assessed to be “possibly related” or “related”.

The number (and percentages) of serious adverse events and participants affected for each type of adverse event will be tabulated. No hypothesis testing will be carried out.

Apart from serious adverse events, other safety endpoints include:

Statistical Analysis Plan		Page 16 of 28
Sponsor Senseonics, Incorporated	Study PROMISE Study: A Prospective, Multicenter Evaluation of Accuracy and Safety of an Implantable Continuous Glucose Sensor Lasting up to 180 Days	Version 3.0

- Incidence rates of device-related or procedure-related (from insertion or removal of the Sensor) adverse events that occurred at home or during clinic visits.
- Incidence rates of any adverse events, serious or not serious, that occurred at home or during clinic visits.
- Incidence rate of hospitalizations due to hypoglycemia, hyperglycemia or ketoacidosis that occurred at home.
- Incidence rate of self-reported episodes of hypoglycemia or hyperglycemia that occurred at home.

For each of the above endpoint, the number (and percentage) of events and participants affected, stratified by age, will be presented as a table. A list of patients affected with information on date of onset, severity, seriousness, relatedness, classification as anticipated or unanticipated, corrective actions and resolution status will be prepared.

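### SAEs of unknown causality are left out of the main safety endpoint as if a link had been ruled out, and the two documents give 'procedure-related' different scopes

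*Protocol*

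**What the plan says.** **Causality grades.** Protocol 9.1 defines four. Two matter here and mean different things: "None: The event is not associated with the device or procedure", and "Unknown: There is no evidence or relevant data available to assess the relationship between the event and the device or procedure".

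**What is assessed.** Protocol 9.1 names three possible causes: "The causal relationship should be determined with respect to the investigational device, the insertion or removal procedure, or other study-related procedures".

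**Endpoint.** Protocol 11.2: "The safety endpoint is the incidence of device-related or insertion/removal procedure-related serious adverse events (SAEs) in the clinic and during home use", through 180 days.

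**Rule for related.** Protocol 11.2: "An Adverse Event is considered 'related' if the relatedness is categorized as 'possibly related', or 'related". SAP 6.6.1 classes an event as related "if its relatedness is assessed to be" one of the same two grades. Both documents use the Medical Monitor's assessment. Neither says what happens to Unknown or to a missing assessment.

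**Reporting groups.** Protocol 11.2 reports SAEs by type, "identified as device-related, procedure-related or unrelated to the study", and also gives the count and proportion of patients with at least one device-related or procedure-related SAE.

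**Scope of 'procedure'.** For SAE reporting, Protocol 9.3 asks for "causal relationship to device and procedure (insertion/removal/other study procedure"). SAP 6.6.1 limits procedure-related to insertion or removal of the Sensor.

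**The concern.** There are two separate gaps.

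The first is the grade Unknown. The safety objective (Protocol 2.2, SAP 3.1.2) is to demonstrate safety from the incidence of related SAEs. The rule counts two of the four grades, so the SAEs about which least is known leave the numerator together with those judged unconnected. The inserted subjects stay in the denominator whatever the grade, so the omission cannot raise the rate and may lower it. No sensitivity analysis is planned.

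The second is the term procedure-related. Protocol 8.5 names IV catheter placement, frequent blood sampling and the glucose challenges as procedures that carry risk. It also says that hypo- and hyperglycemia are not reported as adverse events unless they meet the SAE criteria, so a challenge-induced glycemic event that is reported as an adverse event will be an SAE. Two analysts working from the same data could report different patient counts for this class of event.

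**Working it through.** The plan states no expected figure for this endpoint, so there is none to reproduce. The zeros in the Appendix 1 safety tables are marked as sample data and are not a forecast.

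**1. How each grade is treated**

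| Grade (Protocol 9.1) | Meaning | Counted as related (Protocol 11.2, SAP 6.6.1)? |
|---|---|---|
| None | link ruled out | no |
| Possibly Related | link possible | yes |
| Related | link likely or established | yes |
| Unknown | nothing available to assess the link | no, by omission |

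A missing assessment has the same fate. SAP 6.3 imputes nothing unless otherwise specified, and a missing data point does not contribute to that part of the analysis.

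**2. Size of the Unknown gap**

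Inputs:
- n = 180 inserted subjects (Protocol 3.3.1).
- x = number of subjects whose only candidate SAE is graded Unknown. The documents give no value, so x = 0 to 3 is an assumption, with no SAE graded possibly related or related.

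The rate is x/n. The exact (Clopper-Pearson) 95% limits are:
- lower: the 2.5th percentile of Beta(x, n − x + 1), or 0 when x = 0;
- upper: the 97.5th percentile of Beta(x + 1, n − x). For x = 0 this is 1 − 0.025^(1/180) = 2.03%.

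| x | Rule as written | Unknown counted as related | Exact 95% limits after counting |
|---|---|---|---|
| 0 | 0/180 = 0.00% | 0/180 = 0.00% | 0 to 2.03% |
| 1 | 0/180 = 0.00% | 1/180 = 0.56% | 0.01 to 3.06% |
| 2 | 0/180 = 0.00% | 2/180 = 1.11% | 0.13 to 3.96% |
| 3 | 0/180 = 0.00% | 3/180 = 1.67% | 0.35 to 4.79% |

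Each such subject moves the endpoint by 1/180 = 0.56 percentage points. The limits only give scale, since the plan makes no inference on this endpoint.

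**3. Scope of 'procedure'**

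| Place | Scope |
|---|---|
| Protocol 9.1, causes assessed | insertion/removal and other study procedures, named separately |
| Protocol 9.3, SAE report | insertion, removal and other study procedure under one word |
| Protocol 11.2, endpoint | insertion/removal only |
| Protocol 11.2, reporting groups and patient count | not qualified |
| SAP 6.6.1 | insertion/removal only |

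Take one assumed SAE caused by a glucose challenge, graded Related to other study procedures and None for the device and for insertion/removal.
- *Endpoint as defined:* not counted, 0/180.
- *Protocol 9.3 meaning:* the SAE goes under procedure-related. The device-or-procedure patient count is 1/180 = 0.56%, which exceeds the defined endpoint.
- *SAP 6.6.1 meaning:* the patient count is 0/180. The only group left in Protocol 11.2 is unrelated to the study, which would be untrue of this event.

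**The case against.** **Unknown should be rare.** Possibly Related is defined broadly in Protocol 9.1, so many doubtful events would land there and be counted. Protocol 13.13 has an independent Medical Monitor assign relatedness for the endpoint, under a Safety Management Plan that is not part of these documents. This stands as an argument about frequency. It does not close the gap: no other grading scale is given for the Monitor, and nothing says that the Monitor may not use Unknown.

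**Nothing is hidden.** Protocol 11.2 also reports all adverse events whatever their cause and lists each AE and SAE with its relatedness. SAP 6.8 tabulates SAEs. This stands, and a reader could find the Unknown events in the listing, but the headline rate would remain uncorrected.

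**No decision depends on it.** The endpoint is descriptive, with no threshold. That limits the consequence to how the rate is reported and read.

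**Counting Unknown as related is only one convention.** True. A sensitivity count would give the same information, and for that reason the fix shows the figure both ways.

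A reader might also infer more than the text supports:
- *That Unknown SAEs will be shown as unrelated to the study.* No text assigns them to any group, and the shell of Table 3 could not be checked. What is established is that they are not counted.
- *That challenge or IV SAEs have no correct place in the tables.* Under the usage in Protocol 9.3 they fit under procedure-related. They lack a place only under the narrower SAP meaning.
- *That they inflate the device figure.* Device-related and procedure-related are separate groups. Only the combined count could grow.
- *That leaving challenge SAEs out of the main endpoint is an error.* The endpoint is explicitly limited to the device and insertion/removal.

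**Conclusion.** The concern holds as two gaps in specification. First, the rule as written gives an unassessable SAE or AE the same effect on the related-event endpoints as one with no link, and the effect runs only in the favourable direction. The same omission applies to a missing assessment. Second, procedure-related has no single meaning, so the combined patient count can differ from the defined endpoint, or SAEs from other study procedures can end up with no truthful group.

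The size is 0.56 percentage points per affected subject with 180 inserted. If no SAE is otherwise related, one Unknown event changes the exact upper limit from 2.03% to 3.06%. This assumes that the Medical Monitor grades on the Protocol 9.1 scale and that at least one such event occurs, which the documents neither predict nor exclude. The point is worth correcting because so few events could alter the headline. It is not evidence that harm would be concealed.

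**What to change.** 1. In Protocol 11.2 and SAP 6.6.1, state that an SAE or AE whose relatedness to the device or to insertion/removal is Unknown or missing counts as related for the main safety endpoint and the related-AE endpoint. Show the number of such events and subjects beside the result, so that the figure without them can be read off.
2. Define procedure-related in both documents as related to sensor insertion or removal, and use it in that sense for the reporting groups and the combined patient count.
3. Add a separate reporting group for SAEs related to other study procedures (glucose challenge, IV line, blood draw), apart from both insertion/removal and unrelated.

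The cost is a few sentences in each document and one extra group in the tables. Investigators already assess causality against all three causes (Protocol 9.1 to 9.3). Protocol 13.13 mentions only device and procedure relatedness for the Medical Monitor, so confirm that the Monitor's form records other study procedures separately. The downside is that the reported related-SAE rate may be slightly less favourable.

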11.3 EFFECTIVENESS ENDPOINTS

11.3.1 SUMMARY

The effectiveness measure will be the mean absolute relative difference (MARD), calculated for all paired Sensor and reference measurements through 180 days post-insertion.

11.3.2 EFFECTIVENESS MEASURE

11.3.2.1 EFFECTIVENESS MEASURE: CRITERIA

The effectiveness objective is to descriptively document the distribution of absolute relative difference across all evaluable subjects and to estimate the MARD. MARD will be calculated based on all the data through 180 days of Sensor use. Descriptive statistics will be provided for the MARD. There is no hypothesis to be tested. No inferential statistical analysis will be performed.

The effectiveness measure is the mean absolute relative difference (MARD), defined as the average of absolute difference of paired Eversense® 180 CGM System and reference glucose readings divided by the reference glucose reading (reference) for all reference glucose values, that is:

$$\text{MARD} = \left(\left(\sum \frac{|(\text{Glucose})_{\text{SENSOR}} - (\text{Glucose})_{\text{REFERENCE}}|}{(\text{Glucose})_{\text{REFERENCE}}} \right) / n \right) \times 100\%,$$

Where, n is the total number of CGM and reference glucose pairs during the evaluation period, that is, through 180 days of Sensor use.

11.3.2.2 SAMPLE SIZE AND POWER CALCULATION

This study does not feature any inferential statistics. The sample size for the study was not determined based on a power calculation but was based on the desire to obtain a minimum number subjects at the 180 day visit (i.e. 120)

Additionally, the enrollment target of 20 patients per subgroup of interest (based on type of diabetes (type 1 vs. type 2), age (≥ 65 years of age vs. < 65), and baseline HbA1c ($\geq 8\%$ vs. $< 8\%$) will provide a clinically reasonable amount of data to characterize these subgroups. A subgroup of size 20 will provide an 80% probability of observing one or more rare events in that subgroup for a subgroup population rate as low as 8%.

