3.3 STUDY DESIGN

3.3.1 OVERVIEW

This is a prospective, multi-center study, whereby approximately 210 subjects will be enrolled, and 180 subjects will be inserted in the United States at up to 15 sites. The investigation will include both clinic visits and home use of the Eversense® 180 CGM System. A minimum of 80 subjects, will have two Sensors inserted by trained Investigators. The Sensor(s) will be inserted in the upper arms of the subjects. The accuracy of the Eversense® 180 CGM System will be evaluated during clinic visits comparing Sensor glucose values and plasma glucose values measured on a bedside glucose analyzer. For qualifying subjects, during the clinic visits, there will be planned hyperglycemia and hypoglycemia challenges, as described in Section 4.3.

In this study, including the clinic and home settings, all diabetes care decisions will be based on SMBG blood glucose values and clinical standard of care, rather than Eversense® 180 CGM System results.

To ensure adequate numbers of subjects for specific scenarios of interest, there will be two randomizations:

- Shift of the Day 1 sensor accuracy assessment: early (hours 1-8) vs. middle (hours 9-16) vs. late (hours 17-24)
- Day of the Visit 4 accuracy assessment: Day 7 vs. Day 14

Shift of the Day 1 assessment will be for the Day 1 of sensor life (the day after insertion). Both randomizations are independent of one another.

The Subject visit schedule includes 12 visits over a period of approximately 8 months (inclusive of visit windows from screening visit through follow-up visit). For the subset of subjects inserted with 2 sensors, the subject visit schedule includes 16 visits over a period of approximately 14 months.

The study is anticipated to take approximately 26 months, including the enrollment period.

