5 GENERAL CONSIDERATIONS FOR STUDY VISITS

5.1 DEFINITION OF ENROLLMENT

A subject is considered enrolled in the clinical trial after he or she has provided informed consent.

Subjects who fail one or more of the eligibility criteria are considered screen failures. Subjects who withdraw consent or are withdrawn by the investigator after enrollment and prior to the first Sensor insertion attempt are “withdrawn prior to Sensor insertion” and are withdrawn from the study without data acquisition. A listing of screen failures and “withdrawals prior to Sensor insertion” subjects including the reason for study exit will be reported.

Subjects who begin a first Sensor insertion procedure (defined as injection of local anesthetic) remain enrolled in the study and will be analyzed as evaluable subjects per the description of study populations in Section 11 Statistical Methods.

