An enrollment target of 20 participants per subgroup of interest (see Section 6.9) should provide sufficient data to characterize these subgroups. The probability of detecting one or more events in a group of 20 participants is 80%, when such event occurs with a probability of 8%.

For the SBA sensor configuration, a total of 43 sensors are planned.

Statistical Analysis Plan		Page 13 of 28
Sponsor Senseonics, Incorporated	Study PROMISE Study: A Prospective, Multicenter Evaluation of Accuracy and Safety of an Implantable Continuous Glucose Sensor Lasting up to 180 Days	Version 3.0

6 Statistical Analyses

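### The 80% chance of seeing an 8% event needs 20 inserted subjects per subgroup, but the target of 20 counts consented subjects; a subgroup just meeting it has about 17 inserted and a 76% chance

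*Protocol*

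**What the plan says.** Protocol 11.3.2.2 explains that the overall sample size does not come from a power calculation. For subgroups (diabetes type, age, baseline HbA1c) it relies on "the enrollment target of 20 patients per subgroup of interest" and adds: "A subgroup of size 20 will provide an 80% probability" of at least one event when the subgroup rate is 8%. SAP Section 5 also sets 20 as an enrolment target, points to Section 6.9 for the list of subgroups, and repeats the 80% and 8% figures for 20 participants.

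Protocol 5.1 defines the term: "A subject is considered enrolled in the clinical trial after he or she has provided informed consent". Protocol 4.1 and SAP 4.1 agree. Screening failures and withdrawals before insertion therefore occur after enrolment, and Protocol 5.1 has those withdrawals leave without any data being acquired.

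Protocol 3.3.1 gives the two totals as separate counts: "approximately 210 subjects will be enrolled, and 180 subjects will be inserted in the United States". Protocol 11.1.6 bases the safety analysis on subjects who undergo insertion. Protocol 7.6.6 and SAP 4.3 say that subjects who exit early are not replaced.

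**The concern.** The target and the probability count different people. The target is met when 20 members of a subgroup have consented. The probability needs 20 members in whom an event can occur and be analysed. A consented subject who never receives a sensor cannot have a device or insertion event. Protocol 9.3.1 does collect adverse events from enrolment, but such a subject is outside the safety population in any case. Neither document raises the 20 to allow for this loss, and neither says that the 20 means inserted subjects.

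The 80% is the only quantitative support given for the subgroup size. If it is overstated, a reader may take more reassurance than is warranted from a small subgroup in which no events were seen.

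**Working it through.** **Inputs**

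- Target: 20 enrolled per subgroup (Protocol 11.3.2.2; SAP Section 5).
- Event rate: 8% (same places).
- Enrolled and inserted totals: about 210 and about 180 (Protocol synopsis and 3.3.1; SAP Section 4).
- Diabetes type: about 70% type 1 (Protocol synopsis).

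**Formula.** With independent subjects and true rate p, the chance of at least one subject with an event among n is 1 − (1 − p)^n. The rate at which this chance equals 80% is 1 − 0.2^(1/n).

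**Step 1: reproduce the plan's figure.** With n = 20 and p = 0.08, 1 − 0.92^20 = 81.1%. This agrees with the stated 80%. The size needed for exactly 80% is ln(0.2)/ln(0.92) = 19.3, so 20 is the smallest whole number that works. At n = 19 the chance is already 79.5%, so there is no room for loss.

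**Step 2: convert 20 enrolled to inserted.** 20 × 180/210 = 17.1, or about 17.

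**Step 3: recompute.**

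| Analysable subjects | Chance of at least one event at 8% | Rate needed for 80% |
|---|---|---|
| 20 | 81.1% | 7.7% |
| 18 | 77.7% | 8.6% |
| 17 | 75.8% | 9.0% |

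Using 17.1 without rounding gives 76.1%, so about 76% either way.

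**Step 4: enrolment needed for 20 inserted.** 20 × 210/180 = 23.3, so 24 enrolled.

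**Step 5: which subgroups are exposed.** Type 2 at about 30% of 210 is about 63 enrolled and 63 × 180/210 = 54 inserted, well above 20. A subgroup sits at its target only if it makes up about 20/210 = 9.5% of enrolment. The documents give no expected counts for the age or HbA1c groups. SAP 6.9 lists an age band of 18 to 20 years, so a subgroup near its target cannot be ruled out, but none is shown to be there.

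**The case against.** The strongest reply is that the probability sentence is conditional on a subgroup of 20 and is correct as written. That stands: there is no error in the binomial calculation. But the sentence is offered to justify the target, and a target met as the documents define it does not supply 20 analysable subjects.

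A second reply is that enrolment is used loosely. The synopsis describes the screening evaluation as deciding eligibility for enrolment, which places enrolment after screening. Protocol 11.1.2 describes selection among eligible subjects, all of whom receive sensors. Baseline HbA1c is drawn at the screening visit, after consent, so membership of that subgroup is not known when a subject consents. These points make it plausible that the authors had eligible or inserted subjects in mind. They do not displace the explicit definition in both documents or the use of 210 and 180 as distinct counts. They are a reason to state which is meant.

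A third reply is that the study is descriptive and numbers of evaluable observations will be reported (SAP 6.3). That stands too, and it limits the weight of the point.

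A reader might go further and divide the minimum of 120 subjects at Day 180 by 210, inferring that only about 11 of 20 remain and that the chance falls to 60%. The documents do not support that reading:

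- Subjects who leave before Day 180 still contribute events up to their exit, and nothing ties the 8% illustration to events visible only in those who complete.
- SAP 6.2 mentions the Day 90 and Day 180 visits in defining the safety population, but the wording is unclear. SAP 6.8 uses subjects followed to the start of the analysis interval as the denominator.
- The 120 is a minimum, not an expected count. The retention implied by Protocol 11.1.4 (112 to 120 of 160 inserted, or 70% to 75%) would give 12 to 13 subjects and 63% to 66%, even if completers were the right group.

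**Conclusion.** The point holds as a minor correction. A subgroup filled only to its enrolment target, as both documents define enrolment, has about a 76% chance of showing at least one event at an 8% rate, against the stated 80% (81.1% computed). Equivalently, the 80% assurance applies to rates of about 9% or more.

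This rests on two assumptions: that the overall ratio of 180 inserted to 210 enrolled applies within each subgroup, and that the subgroup only just reaches 20. If fewer subjects are lost before insertion, the gap is smaller. If the subgroup is well above 20, as type 2 should be, there is no gap. No hypothesis test, endpoint or overall sample size changes.

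**What to change.** In Protocol 11.3.2.2 and SAP Section 5, do one of the following:

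- Define the target as 20 inserted subjects per subgroup. The 80% figure can then stay. At the plan's own ratio this means about 24 enrolled in any subgroup that would otherwise stop at 20.
- Keep 20 enrolled and restate the probability as about 76% at an 8% rate, or 80% at a rate of about 9%, noting the assumed ratio of 180 to 210.

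The second option costs one sentence in each document and no subjects. The first is a change of wording and needs extra enrolment only in a subgroup that would fall short of 20 inserted.
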